#### **4.4 Selection of Study Population**

##### **4.4.1 Inclusion Criteria**

Subjects must fulfill all of the following inclusion criteria to be eligible for participation in the study:

1. Participants legally competent to read, write, and sign and give informed consent, or, in the case of adolescents, assent with consent of a parent(s) or legal guardian, as required by local laws.
2. Males and females ages 12 years and older (inclusive) at the time of consent or assent (for adolescents)
3. Scalp psoriasis with an Investigator Global Assessment of Scalp disease severity (S-IGA) of at least Moderate ('3') at Baseline
4. Extent of scalp psoriasis involving  $\geq 10\%$  of the total scalp at Baseline
5. A Psoriasis Scalp Severity Index (PSSI) score of at least 6 at Baseline.
6. An IGA of body (i.e., non-scalp) psoriasis (B-IGA) of at least Mild ('2') at Baseline
7. A PASI score of at least 2 (excluding the palms, and soles) at Baseline
8. Clinical diagnosis of psoriasis vulgaris of at least 6 months duration as determined by the Investigator. Stable disease for the past 4 weeks.
9. Psoriasis involvement on scalp and non-scalp areas totaling  $\leq 25\%$  BSA (not including palms/soles)
10. Females of childbearing potential (FOCBP) must have a negative serum pregnancy test at Screening (Visit 1) and a negative urine Baseline (Visit 2). In addition, sexually active FOCBP must agree to use at least one form of an acceptable effective contraception throughout the trial. Acceptable effective forms of contraception may include: combine estrogen and progesterone containing hormonal contraception associated with inhibition of ovulation (oral, intravaginal, transdermal); progesterone only contraception associated with inhibition of ovulation (oral, injectable, implantable); intrauterine device, intrauterine hormone releasing system, bilateral tubal occlusion, and partner's vasectomy. If barrier methods are used (e.g., condom with spermicide, diaphragm with spermicide), then 2 forms of conception are required. The use of abstinence as a contraceptive measure is acceptable as long as this is the preferred and usual lifestyle choice of the subject and a backup method has been identified if the subject becomes sexually active.

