4.2. Interim Analysis and Data Monitoring

No interim efficacy analyses are planned.

5. Analysis Populations

The following analysis populations are planned for this study:

- **Safety Population (SAF):** The Safety population will include all subjects who are enrolled and received at least 1 confirmed dose of investigational product (IP). This population will be used for all safety analyses.
- **Intent-To-Treat Population (ITT):** The ITT population will include all randomized subjects. This population will be the primary analysis population for the analysis of efficacy endpoints, along with subject disposition.
- **Modified Intent-To-Treat Population (mITT):** The mITT population includes all randomized subjects with the exception of subjects who missed the Week 8 S-IGA assessment specifically due to novel coronavirus disease-19 (COVID-19) disruptions. This population will be the sensitivity analysis population for the analysis of primary and secondary efficacy endpoints.
- **Scalp Pruritus ITT Population (SPRU4-ITT):** The SPRU4-ITT population is a subset of the ITT population and includes subjects with SI-NRS score ≥ 4 at baseline. This population will be used for the analysis of achievement of a 4-point reduction in SI-NRS score as compared to baseline for this subset of ITT subjects.
- **Scalp Pruritus mITT Population (SPRU4-mITT):** The SPRU4-mITT population is a subset of the mITT population and includes subjects with SI-NRS score ≥ 4 at baseline. This population will be used for the analysis of achievement of a 4-point reduction in SI-NRS score as compared to baseline for this subset of mITT subjects.
- **Pruritus ITT Population (PRU4-ITT):** The PRU4-ITT population is a subset of the ITT population and includes subjects with WI-NRS score ≥ 4 at baseline. This population will be used for the analysis of achievement of a 4-point reduction in WI-NRS score as compared to baseline for this subset of ITT subjects.
- **Pruritus mITT Population (PRU4-mITT):** The PRU4-mITT population is a subset of the mITT population and includes subjects with WI-NRS score ≥ 4 at baseline. This population will be used for the analysis of achievement of a 4-point reduction in WI-NRS score as compared to baseline for this subset of mITT subjects.

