- **CDLQI Score** = sum of the 10 questions (individual questions scored as Very much=3, Quite a lot=2, Only a little=1, Not at all=0; Question 7: if the last week was school time, the question was scored as Very much=3, Quite a lot=2, Only a little=1, Not at all=0, with Prevented school recoded to 3, and if the last week was vacation, the standard responses apply; range for score 0 to 30). If 1 item is missing, that item is scored as 0. If 2 or more items are missing, the score should not be calculated.

- **PSD Total score** = sum of the 16 questions (individual questions scored 0 to 10, where higher scores indicate more severe symptoms; range for total score 0 to 160). If 1 or more items are missing, the score is not calculated.
- **Compliance** = number of applications divided by the expected number of IP applications for each subject. Compliance will be calculated using drug accountability data over the entire treatment period for each subject, up to treatment completion or discontinuation.
 - **Number of expected IP applications** = 56 for subjects who complete the study or number of days between first and last application of IP (last treatment date - first treatment date + 1) for subjects who discontinue early from the study.
 - **Number of IP applications** = number of expected IP applications – missed IP applications as collected in the electronic case report form (eCRF).
- **Weight of IP (g)** = returned can weight – dispensed can weight.
- **Body mass index (BMI) (kg/m²)** = [weight (kg) / height (cm) / height (cm)] x 10,000.
- **BMI Categories**
 - Underweight: BMI < 18.5
 - Normal: 18.5 ≤ BMI ≤ 24.9
 - Overweight: 25.0 ≤ BMI ≤ 29.9
 - Obese: BMI ≥ 30.0
- **Change from baseline** = value at current time point – value at baseline.
- **Treatment emergent AE (TEAE)** = any AE with an onset date/time after the first application of IP.
- **PHQ-8** = sum of the 8 questions (individual questions scored as Not at all=0, Several days=1, More than half the days=2, and Nearly every day=3; range for score 0 to 24). If more than 1 item is missing, the score should not be calculated. If 1 item is missing, the score is calculated as (sum of answered items*8)/number of answered items.

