8.3. Exploratory Efficacy Analysis

Exploratory efficacy analysis will be performed for subjects belonging to ITT and mITT populations.

The exploratory endpoints include:

- Achievement of success in PASI-90, PASI-75, and PASI-50 at Weeks 2, 4, 8, and 9
- Time to success in PASI-50
- Change and percent change from baseline in PASI/mPASI at Weeks 2, 4, 8, and 9
- Change and percent change from baseline in WI-NRS at Weeks 2, 4, and 8
- For subjects with baseline WI-NRS score ≥ 4 , achievement of ≥ 4 -point improvement from baseline in WI-NRS at Weeks 2, 4, and 8 (summarized on the PRU4-ITT and PRU4-mITT populations)

- Change and percent change from baseline in DLQI/CDLQI total scores at Weeks 2, 4, and 8
- Change and percent change from baseline in % BSA affected by disease at Weeks 2, 4, 8, and 9

Time to success in PASI-50 and change and percent change from baseline for all relevant exploratory endpoints will be summarized descriptively; additionally, all endpoints will be analyzed using an ANCOVA with terms for country, baseline S-IGA category, and baseline B-IGA category, and baseline assessment score as a covariate. Statistical comparisons between the treatment groups will be obtained using contrasts. The LS means, standard errors, 95% CIs, and *P* values will be presented. Achievement of success in PASI-50, PASI-75, and PASI-90; achievement of success in mPASI-50, mPASI-75, and mPASI-90; and improvement in WI-NRS will be presented using proportions. Odds ratios and 95% CIs of the odds ratios will be provided. Additionally, the 95% Wilson CIs for proportion of successes in each treatment group will be presented.

For efficacy analysis purposes, the data that is collected by the ePRO will be used for % BSA affected by disease summarization.

9. Safety and Tolerability Analysis

Safety will be evaluated from reported AEs, physical examinations, local tolerability assessments, changes in clinical laboratory values, changes in vital signs/weight, C-SSRS, PHQ-8, and modified PHQ-A results. No inferential statistical tests will be performed.

All safety analyses will be performed on the Safety population.

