9.4. Vital Signs

Descriptive summaries of observed values and changes from baseline will be calculated for systolic blood pressure, diastolic blood pressure, heart rate, height, weight, BMI, and oral body temperature by treatment group and visit.

The number of subjects who gain or lose $\geq 5\%$ of their baseline body weight during the course of the study, as well as subjects who gain or lose $\geq 10\%$ of their baseline body weight over the course of the study, will be summarized by treatment group. This summary will be repeated by intentionality of weight loss (intentional or unintentional, as captured on the eCRF).

Shift tables for subjects who shift from their baseline BMI category as defined in Section 6.1.7 (underweight, normal, overweight, obese) to a different BMI category throughout the course of the study will be provided by treatment group and visit. This summary will be repeated by intentionality of weight loss (intentional or unintentional, as captured on the eCRF).

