14.3.6 Other Safety Data Summary Tables		
Table 14.3.6.1	Safety	Shift from Baseline in Patient Health Questionnaire (PHQ-8)/Modified PHQ-Adolescents by Study Visit
Table 14.3.6.2.1	Safety	Summary of Investigator Local Tolerability Assessment by Study Visit
Table 14.3.6.2.2	Safety	Summary of Investigator Local Tolerability Assessment (Dermal Response) by Study Visit Categorical Results
Table 14.3.6.2.3	Safety	Summary of Investigator Local Tolerability Assessment (Other Effects) by Study Visit Categorical Results
Table 14.3.6.3.1	Safety	Summary of Subject Local Tolerability Assessment by Study Visit
Table 14.3.6.3.2	Safety	Summary of Subject Local Tolerability Assessment by Study Visit Categorical Results
Table 14.3.6.4.1	Safety	Summary of Vital Signs by Study Visit
Table 14.3.6.4.2	Safety	Shift from Baseline in Weight by Study Visit
Table 14.3.6.4.3	Safety	Shift from Baseline in Weight by Study Visit and Weight Loss Intentional/Non-Intentional Categories
Table 14.3.6.4.4	Safety	Shift from Baseline in BMI Categories by Study Visit
Table 14.3.6.4.5	Safety	Shift from Baseline in BMI Categories by Study Visit and Weight Loss Intentional/Non-Intentional Categories
Table 14.3.6.5	Safety	Summary of Columbia-Suicide Severity Rating Scale (C-SSRS) Suicidal Ideation and Suicidal Behavior by Study Visit
Table 14.3.6.6	Safety	Summary of Physical Examination by Study Visit
Table 14.3.6.7	Safety	Summary of Concomitant Medications by ATC Class Level 4 and Preferred Term

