Note: Percentages are n/Number of subjects in the Safety population within treatment received and overall*100. Baseline is the last non-missing measurement taken before the first application of study drug.
 Reference Listing: 16.2.9.3.2

Table 14.3.6.4.3
Shift from Baseline in Weight by Study Visit and Weight Loss Intentional/Non-Intentional Categories
Safety Population

(Same shell as Table 14.3.6.4.2, except will be presented by the following categories as headers in the by-line: “Weight Loss: Intentional” and “Weight Loss: Not Intentional or Missing”).

Table 14.3.6.4.4
Shift from Baseline in BMI Categories by Study Visit
Safety Population

Study Visit	Post-Baseline Category [1]	Baseline Category Roflumilast Foam 0.3% (N=XX)				Total
		Missing	Underweight	Normal	Overweight	
Week 2	Missing	XX (XX.X%)	XX (XX.X%)	XX (XX.X%)	XX (XX.X%)	XX (XX.X%)
	Underweight	XX (XX.X%)	XX (XX.X%)	XX (XX.X%)	XX (XX.X%)	XX (XX.X%)
	Normal	XX (XX.X%)	XX (XX.X%)	XX (XX.X%)	XX (XX.X%)	XX (XX.X%)
	Overweight	XX (XX.X%)	XX (XX.X%)	XX (XX.X%)	XX (XX.X%)	XX (XX.X%)
	Obese	XX (XX.X%)	XX (XX.X%)	XX (XX.X%)	XX (XX.X%)	XX (XX.X%)
Total	XX (XX.X%)	XX (XX.X%)	XX (XX.X%)	XX (XX.X%)	XX (XX.X%)	XX (XX.X%)
Week 4	Missing	XX (XX.X%)	XX (XX.X%)	XX (XX.X%)	XX (XX.X%)	XX (XX.X%)
	Underweight	XX (XX.X%)	XX (XX.X%)	XX (XX.X%)	XX (XX.X%)	XX (XX.X%)
	Normal	XX (XX.X%)	XX (XX.X%)	XX (XX.X%)	XX (XX.X%)	XX (XX.X%)
	Overweight	XX (XX.X%)	XX (XX.X%)	XX (XX.X%)	XX (XX.X%)	XX (XX.X%)
	Obese	XX (XX.X%)	XX (XX.X%)	XX (XX.X%)	XX (XX.X%)	XX (XX.X%)
Total	XX (XX.X%)	XX (XX.X%)	XX (XX.X%)	XX (XX.X%)	XX (XX.X%)	XX (XX.X%)

Repeat for Vehicle and Overall. Repeat all for Week 8.

Abbreviation: BMI = body mass index.

Note: Percentages are n/Number of subjects in the Safety population within treatment received and overall*100. Baseline is the last non-missing measurement taken before the first application of study drug. BMI is derived as (weight in kg)/[(height in cm/100)²].

[1] If BMI is below 18.5 then it is categorized as underweight; if BMI ranges between 18.5 – 24.9 then it is categorized as Normal; if BMI ranges between 25.0 – 29.9 then it is categorized as overweight; if BMI is ≥ 30.0 then it is categorized as obese.

Reference Listings: 16.2.9.4.1, 16.2.9.4.2

Table 14.3.6.4.5
Shift from Baseline in Weight by Study Visit and Weight Loss Intentional/Non-Intentional Categories
Safety Population

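### Fixed BMI categories with no age limit give adult weight-status labels to subjects aged 12 to 17 in two safety shift tables

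*SAP*

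**What the plan says.** The rule and its reach are set in several places.

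- **Definition.** SAP 6.1.7 lists four categories: "Underweight: BMI < 18.5", then normal from 18.5 to 24.9, overweight from 25.0 to 29.9, and obese from 30.0. No age or sex condition is attached.
- **Use.** SAP 9.4 asks for "Shift tables for subjects who shift from their baseline BMI category as defined in Section 6.1.7 (underweight, normal, overweight, obese") by treatment group and visit, and again by whether weight loss was intended.
- **Tables.** Table 14.3.6.4.4 gives the shifts. Its footnote repeats the rule: "If BMI is below 18.5 then it is categorized as underweight". Its denominator note reads "Percentages are n/Number of subjects in the Safety population within treatment received and overall*100". Table 14.3.6.4.5 is listed in SAP 13.1.3 as "Shift from Baseline in BMI Categories by Study Visit and Weight Loss Intentional/Non-Intentional Categories".
- **Population.** SAP Section 9 states "All safety analyses will be performed on the Safety population". SAP Section 5 defines that set: "The Safety population will include all subjects who are enrolled and received at least 1 confirmed dose of investigational product (IP").
- **Ages enrolled.** Protocol 4.4.1, criterion 2, admits "Males and females ages 12 years and older (inclusive) at the time of consent or assent (for adolescents").

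The SAP has an age category of 12-17 versus 18 and over (SAP 7.3), but does not use it in the BMI tables.

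**The concern.** In adolescents the usual range of BMI depends on age and sex, so one set of adult cut-offs does not describe weight status at ages 12 to 17. This is general clinical knowledge, not something the documents state. Applied as written, the rule can label a 12-year-old underweight by an adult standard, and the pooled table gives no age by which to recognise that entry.

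The label matters to a safety reader. Protocol 3.3.2 names weight loss among the commonest adverse events of oral roflumilast, and Protocol 3.4.2 lists it among the effects the trial is designed to detect. SAP Section 10 shows that the BMI shift tables were added at the sponsor's request. Entries in or into the underweight category are the ones such a reader will look for first.

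**Working it through.** The plan gives no figure on this point to reproduce. The check is a reading of the text, followed by arithmetic to show how the rule acts.

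**1. Does any text limit the rule by age?** The places that could do so are the definition (SAP 6.1.7), the analysis text (SAP Section 9 and 9.4), the list of additions (SAP Section 10), the table list (SAP 13.1.3) and the shells (SAP 14.2). None restricts the BMI categories to adults, splits the tables by age, or gives separate criteria for ages 12 to 17. No sentence names adolescents in these tables either. Their inclusion follows from the population definition and the entry age.

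**2. What weight does the lowest cut-off imply?** Weight at BMI 18.5 is 18.5 × (height in metres)². The heights are chosen for illustration.

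- 145 cm: 18.5 × 2.1025 = 38.9 kg
- 150 cm: 18.5 × 2.2500 = 41.6 kg
- 160 cm: 18.5 × 2.5600 = 47.4 kg

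A subject of 150 cm and 40 kg has BMI 40 / 2.25 = 17.8 and is labelled underweight whether aged 12 or 40. These figures restate the cut-off in kilograms. They do not show how many adolescents would be mislabelled.

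**3. Label or shift?** A subject who is in the same category at baseline and at a later visit is not counted as a shift, even if the label does not fit. A crossing needs a BMI close to a cut-off. At 150 cm, 42 kg gives 42 / 2.25 = 18.67 (normal) and 41 kg gives 41 / 2.25 = 18.22 (underweight). That is a loss of 1 / 42 = 2.4%, below the 5% weight-loss threshold, yet it appears as a move into the underweight category.

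**4. How many subjects could carry such labels?** The documents do not state the number of adolescents. The shares below are assumptions, applied to the planned 300 subjects (200 active, 100 vehicle).

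| Assumed share aged 12-17 | Total | Active | Vehicle |
|---|---|---|---|
| 1% | 3 | 2 | 1 |
| 5% | 15 | 10 | 5 |
| 10% | 30 | 20 | 10 |

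These are adolescents classified by the rule, which is an upper limit on those misclassified. One subject moves a percentage by 1/200 = 0.5 points on active and 1/100 = 1.0 point on vehicle.

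**The case against.** The strongest reply is that nothing turns on these categories. Individual safety action uses 5% weight loss (Protocol 1.3, 4.4.3 and 5.1.4). The protocol's own planned displays use weight change above 5% and above 10% (Protocol 6.4.6), and SAP 9.4 keeps such displays. Both arms are classified by the same thresholds, each subject is compared with their own baseline, and crossing a fixed threshold is still a real change in BMI. SAP Section 9 plans no inferential test on safety data. Age, BMI by visit and weight are all in subject listings, so an adolescent entry can be traced. All of this stands, and it is why the point is minor. It does not make the labels right for ages 12 to 17, and the pooled table alone does not show which entries they are.

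Three stronger readings are tempting, and the documents do not support them.

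- *A reader might infer that the treatment comparison is biased or that the shift counts are largely false.* The rule is the same in both arms, and a label that does not change between visits is not a shift.
- *A reader might infer that growth in height produces spurious moves into the underweight category*, because height is measured again at Week 8 and that value enters the Week 8 and Week 9 BMI (Listing 16.2.9.3.1). The documents give no growth rates. Using the current height is the correct way to compute BMI, and any such effect over 8 weeks would be confined to a very narrow band just above the cut-off.
- *A reader might infer that the SAP accepts the need for age-specific thresholds because it tabulates PHQ-8 and PHQ-A separately.* Those are different questionnaires, and SAP 9.5 applies the same severity bands to both. That supports separate display at most.

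A further objection is that taking adolescents out of a safety display has a cost of its own, given the known weight effect of the oral drug. This is right, and the fix below keeps them in view.

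**Conclusion.** The point holds as a minor one. The SAP states a rule that, followed as written, gives adult weight-status labels to subjects aged 12 to 17 in Tables 14.3.6.4.4 and 14.3.6.4.5. The reading of the text is firm. The step from there to labels that do not fit rests on general clinical knowledge about BMI in adolescence, which the documents do not address.

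The effect is limited to labels and occasional category crossings in two descriptive safety tables. Its size cannot be calculated without the number of adolescents, and is probably small in the pooled percentages. No safety decision or hypothesis test uses these categories.

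**What to change.** In SAP 6.1.7 and 9.4, state that the BMI category labels apply only to subjects aged 18 or over at Screening, and base the percentages in Tables 14.3.6.4.4 and 14.3.6.4.5 on that group. Age at Screening is already held (Listing 16.2.4.1.1).

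Present ages 12 to 17 separately, using the SAP 7.3 age category. Show their change in BMI and weight, and the counts with gain or loss of at least 5% and at least 10%, in place of the adult categories.

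The cost is a line in each of the two sections, a new denominator note for Table 14.3.6.4.4, and an age split of summaries already planned. No new data are needed. Table 14.3.6.4.5 has no note of its own: its shell is titled as a weight table and points to itself. The same edit should give it the BMI title from SAP 13.1.3 and refer it to Table 14.3.6.4.4. The downside is that the adolescent displays may have few subjects per cell.

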#### **4.4.3 Removal of Subjects from Investigational Product**

A subject may discontinue from receiving the IP for any of the following reasons:

1. Occurrence of any medical condition or circumstance that, in the opinion of the Investigator, exposes the subject to substantial risk and/or does not allow the subject to adhere to the requirements of the Protocol.
2. Occurrence of a treatment-emergent adverse event (TEAE) or considerable worsening of an AE that, in the opinion of the investigator in consultation with the Medical Monitor and Sponsor, represents an unacceptable risk to the subject if he/she continues in the study. The investigator must follow the subject until the AE resolves or satisfactorily stabilizes.
3. Pregnancy.
4. Subject's decision to withdraw from administration of the IP.
5. Weight loss of >5% if not dieting and after consultation with the Sponsor, at the Investigator's discretion.
6. C-SSRS indicative of suicidal ideation or a PHQ-8 or modified PHQ-A score  $\geq 15$ , after consultation with a mental health professional, the Sponsor, and at the Investigator's discretion.
7. Requirement for use of prohibited concomitant medication (see [Table 1](#)) after consultation with the Sponsor and Medical Monitor.
8. Subject's repeated failure to comply with protocol requirements or study related procedures.

9. The subject interrupts trial IP application for more than 50% of scheduled doses.

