#### 5.1.10 Adverse Events

Adverse events (AEs) will be collected beginning at informed consent and assessed at the following visits and throughout the study:

Screening, Baseline, Weeks 2, 4, 8, and 9

Any treatment emergent AEs will be followed in the clinic for up to one month at the Investigator's discretion until resolved or otherwise judged as clinically stable.

For further details on Adverse Events please see [Section 5.7](#).

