## **5.7 Adverse Events**

### **5.7.1 Adverse Event Definition**

An AE means any untoward medical occurrence associated with the use of a drug in humans, whether or not considered IP related. An AE can therefore be any unfavorable and unintended sign (including an abnormal laboratory finding), symptom, or disease temporally associated with the use of a medicinal (investigational) product, whether or not related to the medicinal (investigational) product.

AEs will be collected following informed consent of the subject through subject study completion.

A treatment emergent adverse event (TEAE) is defined as an AE that started post application of IP at the Baseline visit through study completion.

Application site reactions will be considered adverse events if they require intervention, suspension or discontinuation of the IP.

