#### 6.4.1 Adverse Events

All treatment-emergent AEs occurring during the study will be recorded and classified on the basis of MedDRA terminology for the safety population. Treatment-emergent AEs are those AEs with an onset on or after the date of study treatment. All treatment-emergent AEs will be summarized by treatment group, the number of subjects reporting treatment-emergent AEs, system organ class, preferred term, severity, relationship, and seriousness.

Serious adverse events (SAEs) will be listed by subject. SAEs will be summarized by treatment group, severity, and relationship to study treatment.

For AEs, each subject will be counted only once within a system organ class or a preferred term using the event with the greatest relationship and greatest severity.

All information pertaining to AEs noted during the study will be listed by subject, detailing the verbatim description given by the Investigator, preferred term, system organ class, start date, stop date, severity, action taken regarding IP, corrective treatment, outcome, and IP relatedness. The event onset will also be shown relative (in number of days) to date of first application. In addition, a listing of subjects who prematurely discontinue from the IP due to adverse events will also be provided.

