9.1. Adverse Events

All AEs, TEAEs, and SAEs will be coded using the MedDRA dictionary version 23.0.

A TEAE is defined as an AE that started post application of IP at the Baseline visit through study completion. An overall summary of TEAEs will be provided; this will present number and percent of subjects who reported at least 1 of the following: TEAE (including all TEAEs, TEAEs by maximum severity, and TEAEs by greatest relationship), SAE, discontinued the study due to a TEAE, or a TEAE resulting in death.

The number and percent of subjects reporting TEAEs, grouped by MedDRA system organ class (SOC) and preferred term, will be tabulated by severity or greatest relationship to study IP and treatment group. In the case of multiple occurrences of the same TEAE within the same subject, each subject will only be counted once for each preferred term. Additionally, the number and percent of subjects reporting related TEAEs will be summarized by MedDRA preferred term and treatment group.

In the summaries showing severity and relationship to study medication the event with the maximum severity (mild < moderate < severe) or strongest relationship (not related < related) will be reported. If a particular event is missing the severity and/or relationship, then the strongest possible severity or relationship will be assumed for analysis (severity = severe, relationship = likely).

In the AE data listings, all AEs will be displayed. Any AEs that are treatment emergent will be flagged.

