9.1.1. Adverse Events Leading to Withdrawal

A summary of incidence rates (frequencies and percentages) of TEAEs leading to withdrawal of study drug by treatment group, SOC, and preferred term will be prepared for the Safety population. Additionally, this table will be repeated for TEAEs leading to withdrawal from the study. No inferential statistical tests will be performed.

A data listing of AEs leading to withdrawal of study drug will also be provided, displaying details of the event(s) captured on the eCRF.

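### The TEAE rule looks only at onset, so a pre-dose AE that worsens on product is missed by the TEAE incidence tables and by both discontinuation tables

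*SAP*

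**What the plan says.** The TEAE rule appears in four places in the main text:

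- SAP 6.1.7: "any AE with an onset date/time after the first application of IP".
- SAP 9.1: "A TEAE is defined as an AE that started post application of IP at the Baseline visit through study completion".
- Protocol 5.7.1: "A treatment emergent adverse event (TEAE) is defined as an AE that started post application of IP at the Baseline visit through study completion".
- Protocol 6.4.1: "Treatment-emergent AEs are those AEs with an onset on or after the date of study treatment".

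The footnote to Listing 16.2.7.1 flags TEAEs on the same timing basis.

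Collection starts well before dosing. Protocol 5.1.10 states: "Adverse events (AEs) will be collected beginning at informed consent". Screening may last up to 4 weeks.

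Protocol 4.4.3, item 2, opens its reason for stopping product with "Occurrence of a treatment-emergent adverse event (TEAE) or considerable worsening of an AE that, in the opinion of the investigator". The rest of that item requires the risk of continuing to be judged unacceptable after consulting the Medical Monitor and the Sponsor.

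For discontinuations, SAP 9.1.1 plans a summary of "TEAEs leading to withdrawal of study drug by treatment group, SOC, and preferred term will be prepared for the Safety population". It continues: "Additionally, this table will be repeated for TEAEs leading to withdrawal from the study". These are Tables 14.3.1.5 and 14.3.1.6.

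**The concern.** A definition based on onset alone treats an AE that began in screening as a pre-treatment event, however much it worsens once product is applied. The protocol foresees this situation. In 4.4.3 it lists worsening of an AE beside occurrence of a TEAE as a ground for stopping product, and the worsening limb is not confined to events that began on treatment. An investigator can therefore stop product for an event that the discontinuation tables cannot count.

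Safety is half of the primary objective, and the rate of AEs leading to drug discontinuation is a main tolerability result. Some worsening is caught elsewhere: depression score, suicidality, weight and laboratory changes each have their own tables. Nausea, diarrhoea and insomnia, which Protocol 3.3.2 names as effects of oral roflumilast, have no tabulated scale of their own here and rely on the AE tables.

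**Working it through.** There is no planned figure to reproduce. The check follows one event through the outputs.

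**Traced event.** A non-serious AE with a complete onset date after consent and before first application. It worsens on product, is kept under its original onset date, and leads to stopping product.

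1. *TEAE status.* Onset precedes the first application, so it is not a TEAE under SAP 6.1.7 or 9.1. Protocol 6.4.1 works by calendar day and would admit a Day 0 pre-dose onset, but not an earlier one. The date conventions in SAP 6.1.8 move only missing or partial onset dates, so a complete date stays where it is.
2. *Record structure.* Protocol 5.7.5 takes an onset date, a maximum severity grade and an outcome for each event, and the outcome may be that the event got worse. Neither document says that a change of grade opens a new AE record.
3. *Incidence tables.* Tables 14.3.1.1 to 14.3.1.7 are TEAE tables. The SAE row in 14.3.1.1 does not reach a non-serious event. The event is in none of them, including 14.3.1.5 (stopping drug) and 14.3.1.6 (leaving the study).
4. *Where it does appear.* In Listing 16.2.7.1 without a TEAE flag, and in the listing numbered Table 14.3.3.1, which covers all AEs leading to drug discontinuation. If it became serious it would reach Tables 14.3.2.1 to 14.3.2.3.
5. *Disposition.* Table 14.1.1 shows an AE as the reason only if the subject left before the Week 8 S-IGA. Under footnote 7, anyone with a Week 8 S-IGA is a completer and no reason is summarized. Protocol 4.4.4 gives three reasons for removal from the study, and an AE is not among them. A subject who stops product for this event and attends Week 8 is therefore in no AE or disposition count.

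**Comparison within the plan.** The synopsis names AEs leading to withdrawal from product as a category of its own, beside treatment-emergent, serious and related AEs, with no stated TEAE limit. SAP 9.1.1 adds that limit, and SAP section 10 does not record it as a change. Table 14.3.3.1 can thus list a discontinuation that Table 14.3.1.5 does not count.

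**Size.**

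- Longest pre-dose share of scheduled AE collection: 28 days of screening, then 63 days to Week 9. 28/(28 + 63) = 28/91 = 30.8%. This is calendar time, not an event rate.
- Effect of one omitted subject, using the planned arm sizes: 1/200 = 0.5 points active; 1/100 = 1.0 point vehicle.
- Assuming 1 to 3 omitted subjects in an arm: 1/200 to 3/200 = 0.5 to 1.5 points active; 1/100 to 3/100 = 1.0 to 3.0 points vehicle.

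**The case against.** The strongest reply is that the gap depends on a data-entry rule that neither document contains. If the eCRF instructions have sites open a new record when an AE worsens, that record has a post-dose onset and is already a TEAE. Some text is compatible with this. Protocol 5.7.1 defines an AE by temporal association with product use. Protocol 6.4.3 captures clinically significant examination changes as AEs. SAP 9.1 expects repeated occurrences of one term within a subject. The point stands as a condition: the gap exists only where the original onset date is kept. It does not remove the concern, because the analysis definition should not depend on an unstated entry convention.

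Second, the events remain visible. Table 14.3.3.1 shows every AE that led to stopping drug, with treatment, term, grade and relationship. Table 14.1.6 may reflect the stop through low compliance or more than three consecutive missed doses, if those doses are recorded. This is true, but a listing and a compliance table do not give AE incidence by arm.

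Third, the affected set is narrow. Eligibility requires good health and excludes recent treated infection, and complaints that predate consent are medical history. The PHQ sleep item bears on insomnia, although only total-score shifts are tabulated. The named drug effects come from the oral product. All of this limits the expected number of events, and the 1 to 3 used above is an assumption. No inferential test is affected, since safety is descriptive.

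**Conclusion.** The concern holds. Applied as written, the TEAE rule leaves a non-serious AE that began between consent and first dose, and worsened on product under its original onset date, out of the TEAE incidence tables and both discontinuation incidence tables. The size is 0.5 points per omitted subject in the active arm and 1.0 point in the vehicle arm, assuming about 200 and 100 subjects in the safety population. The number of such events cannot be derived from the documents and is probably small. There is no basis for claiming a direction of bias between arms, and no efficacy conclusion is affected. It is a modest gap in the safety summaries that should be closed before unblinding.

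**What to change.** 1. In SAP 6.1.7 and 9.1, and in Protocol 5.7.1 and 6.4.1, define a TEAE as an AE that starts after the first application of product, or one already present that increases in CTCAE grade or becomes serious after it. State how such a change of grade is recorded.
2. Base Tables 14.3.1.5 and 14.3.1.6, and the drug-discontinuation row of Table 14.3.1.1, on all AEs leading to withdrawal of study drug or from the study after first application, whatever the onset date. Retitle them accordingly. This also brings Table 14.3.1.5 into line with the synopsis and with Table 14.3.3.1.

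The second change needs programming only, because action taken with study drug and study discontinuation are already fields in Listing 16.2.7.1. The first may need site queries to date grade changes, limited to AEs that began before first dose and were still ongoing at that point. The downside is slightly higher TEAE counts.
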